2.1 Study Design

This was a researcher-initiated, multicenter, randomized controlled trial conducted in six first-class general hospitals in China's Zhejiang, Fujian, Jiangsu, and Liaoning provinces. Twelve IV nurse specialists were involved in performing the catheterizations. The research protocol was based on assigning patients to three different catheter tip placement groups and observing the relationship between tip placement and catheter-related complications. The institutional review board approved the research protocol of each participating hospital according to the Helsinki Declaration that respects individuals and recognizes vulnerable groups. All the participants had the right to make informed decisions. (IRB:20200107-11). Patients who underwent MC placement in all six hospitals were enrolled, and the study was conducted between September 2020 and January 2021.

2.2 Participants

A fixed-point continuous convenience sampling method was adopted to enroll 330 participants. The participants who met the clinical criteria for this study were informed about the study and written informed consent was obtained from each participant. Consent may also have been obtained from legally authorized persons. The inclusion criteria were as follows ① estimated time of intravenous infusion ≥ 1 week before catheterization; ② age: ≥ 18 years; ③ antimicrobial therapy was only used for treatment during hospitalization, with a pH value of 5–9 and osmotic pressure < 900 mOsm/L; and ④ patients were conscious and able to communicate normally. ⑤ The catheter-to-vessel ratio is less than 45%. The exclusion criteria were as follows: ① a history of radiotherapy, thrombosis, and trauma at the catheterization site and ② plans to discharge with a catheter during the study duration. Withdrawal criteria were as follows: ① active discharge from the hospital during indwelling of the catheter; ② failure to be followed-up after catheterization due to disease; and ③ a change in health status during antimicrobial therapy treatment, requiring other drugs to be infused treatment through the MC.

2.3 Sampling

A general formula-based sample estimation method using the data on the relationship between MC tip position and catheter-related complications was used to calculate the sample size (Wu et al., 2020). Based on the selected reference, the incidence of complications at the tip of the MC at the thoracic wall of the axillary vein was 32.5% (Wu et al., 2020), while the incidence of complications in the subclavian vein was 12.5% (Wu et al., 2020). A power analysis was performed to calculate the effect size. Efficacy was set at 0.8 (with an 80% probability of finding a difference between populations) and 0.05 (5% of Type I error). Considering external factors that may have caused loss and withdrawal, each group was increased in size by 20%, to 65 patients per group.

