2.4 Randomization and Grouping

There were 428 eligible patients, and 330 consented to participating in this study. A random sequence was generated after participants were recruited, and participants were randomized into three groups using a computerized random number generation

technique. Then, a proportional allocation of treatment methods was adopted to equalize the participants in all groups. Microsoft Excel generated 1000 random integers and 330 corresponding numbers were drawn. The 330 corresponding numbers were arranged into opaque and sequentially numbered envelopes. Then, the envelopes were sorted by random sequence and evenly distributed among the six selected hospitals. Three different study groups with equal numbers of participants (n=110) were established using this non-stratified random allocations.

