**Midline Catheter Tip Positioning and Catheter-Related Complications during
Antimicrobial Therapy: A Multicenter Randomized Controlled Trial**

NCT04601597

April 30, 2021

The current study followed the conformance study protocol analysis and conducted the statistical analysis using SAS 9.4 (<http://www.sas.com/>). The catheter measurement data were represented by mean and standard deviation according to the normal distribution. In contrast, the catheter measurement data with non-normal distribution were represented by median and quartile, and the number of cases or percentages represented the counting data. The catheter-measurement data between the three groups were compared through variance analysis or the Kruskal-Wallis H test. Counting data were compared using the Chi-square test, exact probability method, and Kruskal-Wallis H test. The test level $\alpha=0.05$ for all three groups was a two-sided test, and $P<0.05$ was considered a statistically significant difference. Bonferroni method was used in pairwise comparison to optimize the significance level. The test levels $\alpha=0.017$ and $P<0.017$ were statistically significant differences. To analyze the rate of complications, cumulative event rates were plotted as Kaplan-Meier curve, and differences in these rates were assessed using log-rank tests, and $P<0.0001$ was considered a statistically significant difference. Mann-Whitney U tests were performed to analyze the differences in observed event times.

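### The stated 65 per group, including a 20% allowance, does not give 80% power for 32.5% vs 12.5% under two-sided 0.05 testing, and its basis and its link to the 110 per group enrolled are not stated

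*Protocol*

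**What the plan says.** Protocol section 2.3 describes the method only as "A general formula-based sample estimation method". It takes two rates from one reference: 32.5% with the tip in the axillary vein at the chest wall and 12.5% with the tip in the subclavian vein. By section 2.5.1 these are Experimental Groups 2 and 1. It continues: "Efficacy was set at 0.8 (with an 80% probability of finding a difference between populations) and 0.05 (5% of Type I error"). To cover loss and withdrawal, "each group was increased in size by 20%, to 65 patients per group". The section gives no formula, sidedness, control-group rate or number before the increase.

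Section 2.2 reports a different size: "A fixed-point continuous convenience sampling method was adopted to enroll 330 participants". Section 2.4 agrees: "Three different study groups with equal numbers of participants (n=110) were established". Neither refers back to 65.

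The SAP sets 0.05 for the overall comparison, which "for all three groups was a two-sided test", and a Bonferroni level of 0.017 for pairwise comparisons.

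**The concern.** Section 2.3 is the only justification of sample size in the documents. Its two rates describe a single pair of groups, and for that pair 65 looks too small to contain both 80% power at two-sided 0.05 and a 20% allowance. If so, the power statement is wrong under the testing that the SAP describes.

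Two further gaps make the paragraph hard to use. It does not say which comparison the 80% refers to in a three-group trial whose pairs are tested at 0.017. And 65 per group is 195 patients in total, whereas 330 were enrolled, with no reason given for the difference. A reader cannot tell whether 110 came from a revised calculation, from the supply of consenting patients, or from something else.

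**Working it through.** **Inputs.** From section 2.3: p1 = 0.325, p2 = 0.125, power 0.80 (z = 0.842), alpha 0.05, 20% increase, 65 per group. From section 2.4: 110 per group. From the SAP: two-sided 0.05 overall (z = 1.960) and 0.017 for pairs, which I take as two-sided (z = 2.387).

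Derived: difference d = 0.20; mean rate 0.225; unpooled variance V = 0.325 × 0.675 + 0.125 × 0.875 = 0.32875; pooled variance W = 2 × 0.225 × 0.775 = 0.34875.

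**Formulas for n per group.**
- Unpooled: (z_alpha + z_beta)² × V / d²
- Pooled under the null only: (z_alpha√W + z_beta√V)² / d²
- Pooled throughout: (z_alpha + z_beta)² × W / d²
- Arcsine: 2(z_alpha + z_beta)² / h², with h = 2·arcsin√0.325 − 2·arcsin√0.125 = 0.490

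**Results before any increase.**

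| Test | Unpooled | Pooled under null | Pooled throughout | Arcsine |
|---|---|---|---|---|
| One-sided 0.05 | 50.8 | 52.8 | 53.9 | 51.4 |
| Two-sided 0.05 | 64.5 | 67.2 | 68.4 | 65.2 |
| Two-sided 0.017 | 85.7 | 89.5 | 90.9 | 86.6 |

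A continuity correction raises these further (76.9 at two-sided 0.05 with the second formula).

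**Trying to reproduce 65.** At two-sided 0.05, rounding up gives 65 to 69. Adding 20% gives 65 × 1.2 = 78 to 69 × 1.2 = 82.8. Dividing by 0.8 gives 81.3 to 86.3. The range is therefore 78 to 87, and no version gives 65 with the increase included.

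Three routes do lead to about 65:
- One-sided 0.05 with the increase: 53.9, rounded up to 54, × 1.2 = 64.8.
- Two-sided 0.05, unpooled, with the 20% left out: 64.5, rounded up to 65.
- A three-group chi-square test (2 degrees of freedom, alpha 0.05, noncentrality 9.63 for 80% power) with an unstated control rate. At 12% it needs 54.2 per group (× 1.2 = 65.1). At 38% it needs 53.5 (× 1.2 = 64.2), and at 37.5% it needs 54.9 (× 1.2 = 65.9). These control rates are my assumptions; the documents give none.

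**Power for the 32.5% vs 12.5% pair.** Normal approximation with pooled variance under the null: Φ[(d√n − z_alpha√W) / √V]. The second figure in each cell is exact enumeration of the uncorrected chi-square test. If 65 includes the allowance, the evaluable number is 65 × 0.8 = 52 or 65 / 1.2 = 54. For 110 it is 110 × 0.8 = 88 or 110 / 1.2 = 92.

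| Evaluable per group | Two-sided 0.05 | Two-sided 0.017 |
|---|---|---|
| 52 | 69.0 / 70.6% | 52.3 / 53.9% |
| 54 | 70.7 / 72.0% | 54.2 / 56.4% |
| 65 | 78.6 / 79.6% | 63.8 / 64.8% |
| 88 | 89.5 / 90.3% | 79.2 / 80.5% |
| 92 | 90.8 / 91.4% | 81.3 / 82.5% |
| 110 | 95.0 / 95.3% | 88.5 / 89.4% |

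At n = 65 the fully unpooled approximation gives 80.3% at 0.05 and 66.5% at 0.017. The choice of approximation moves these figures by a few points at most.

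**The case against.** The strongest reply is that 65 is not an arithmetical impossibility. Section 2.3 does not state sidedness, and a one-sided 0.05 calculation with the increase gives 65. The two-sided requirement comes from the SAP, where it is written for the three-group test. This stands in part. A reader might infer that the sponsor miscalculated, or that a one-sided test was used, and the documents establish neither. What remains is that the 80% in section 2.3 does not carry over to two-sided testing of the pair whose rates it quotes.

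A second reply is that section 2.3 claims 80% at 0.05 and says nothing of 0.017. That is correct. The 64-65% at 0.017 with 65 per group therefore contradicts no claim in the plan. It shows only that the sizing took no account of the level at which the SAP tests pairs.

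A third reply is that 110 per group were enrolled, so the shortfall belongs to a size that was not used. This also stands. A reader might infer an underpowered trial, and the figures for 110 rule that out for this pair. A two-sided 0.017 calculation with 20% added even comes out at 110 (90.9, rounded up to 91; 91 × 1.2 = 109.2). But the documents do not say that 110 was obtained in this way, so it cannot be credited as the basis.

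**Conclusion.** The point holds as a wrong and untraceable stated basis for size. It does not show that the trial is too small. Under two-sided 0.05, 65 per group including the 20% allowance falls short of the 78 to 87 needed for 32.5% vs 12.5%, by 13 to 22 patients per group. The loss is about 8 to 11 percentage points of power if the allowance is used up, and at most about one point if nobody is lost.

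This rests on taking the pair in section 2.3 as the target and on an uncorrected chi-square or normal-approximation test. If the SAP's exact method means Fisher's test, power with 65 evaluable is lower (73% at 0.05). If the 80% was meant for the three-group test, it cannot be checked without a control rate. For the same reason, adequacy of 110 per group is shown only for this one pair and not for the two comparisons with control.

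The matter is worth correcting because it is the plan's only sample-size statement, but it does not affect the analysis.

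**What to change.** In section 2.3, restate the calculation actually made: formula, one- or two-sided, alpha, any control rate used, and the number per group before the 20% increase. A one-sided test should not be stated unless one was used.

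Then correct the figure, for example: *At two-sided 0.05, 32.5% vs 12.5% needs 65 to 69 per group for 80% power, or 78 to 87 with the 20% allowance; 65 per group including the allowance does not give 80%.*

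Say when and why 110 per group was adopted. Section 2.1 reports that "the study was conducted between September 2020 and January 2021", so any power now quoted for 110 must be labelled as a recalculation after enrolment: *110 per group gives 88-89% power for Experimental Group 1 vs Experimental Group 2 at two-sided 0.017, and about 79-82% with 88 to 92 evaluable.* Claim no power for comparisons with control unless a control rate was in fact used; if it was, give the rate and the resulting power.

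The cost is one rewritten paragraph, with no extra patients and no change to the analysis. The downside is a less favourable statement for 65 per group.

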2.4 Randomization and Grouping

There were 428 eligible patients, and 330 consented to participating in this study. A random sequence was generated after participants were recruited, and participants were randomized into three groups using a computerized random number generation

technique. Then, a proportional allocation of treatment methods was adopted to equalize the participants in all groups. Microsoft Excel generated 1000 random integers and 330 corresponding numbers were drawn. The 330 corresponding numbers were arranged into opaque and sequentially numbered envelopes. Then, the envelopes were sorted by random sequence and evenly distributed among the six selected hospitals. Three different study groups with equal numbers of participants (n=110) were established using this non-stratified random allocations.

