2.5.2 Catheter Insertion Procedure

A fixed routine for pre-insertion cleaning and equipment was followed, including hand washing, placing the patient in the supine position, skin antisepsis, and preparation of the sterile field. Catheter insertion was performed by senior nurses in the intravenous treatment room, which was a standardized setting for venipuncture. Conventional catheter placement and maintenance methods were adopted as follows: ① evaluation: physicians confirmed the condition of the pre-puncture intima through ultrasound before catheterization. If ultrasound imaging did not show endothelium abnormalities, such as rough intima, it was noted as a smooth standard. Subsequently, 12 catheterization nurses selected the puncture site guided by ultrasound. Nurses took 1/3 of the middle part of the patient's upper arm as the best puncture area and used ultrasound to measure the diameter of the vessel (Chen et al., 2018). ② Catheterization: each hospital assigned two senior IV nurses for MC puncture and measured the catheter pre-placement length according to the measurement method of different groups, and the catheter was placed using ultrasound-guided and modified Seldinger techniques. After confirming the position of the tip, the catheter was trimmed, and the extension sets was connected, with the length of the external catheter were 3 cm. ③ Maintenance: 24 IV specialist nurses were trained to monitor and evaluate catheter functioning weekly, and clinical nurses conducted routine maintenance until study completion. Daily data were recorded and updated to computerized data records.

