2.7 Data Collection

Catheterization nurses recorded baseline data prior to catheterization, and only the most recent results were recorded one week prior to catheterization, when multiple laboratory results were available. Catheterization site evaluations were recorded after placement, and patients were followed up for 48 h after catheterization as well as every 7th day by IV specialist nurses to review and record the progress of antimicrobial therapy. The last follow-up was conducted at the time of removal, where the reason for removal was also recorded. In addition, bedside nurses evaluated and recorded catheter functioning and complications daily.

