2.8 Quality Control

Quality standards and controls were maintained throughout the study. All hospitals included in this study used the same brand and batch number of silicone-valved catheters, with a total length of 30 cm. Catheters could be trimmed to ensure a consistent length of the external catheter and a unified catheter placement and maintenance process. The same criteria were used to appoint IV specialized nurses in each hospital. Only those who had more than three years of PICC or MC

placement experience and more than 200 cases of catheterization were assigned. After catheterization, the evaluation video for catheter-related complications was sent to the nurse managers of the department in which the participants were located. Bedside nurses were trained and assessed by a nurse manager in the department. Researchers with unified training collected the relevant data, followed up, and stored the data in a dedicated electronic database. One researcher was assigned to check the data entries from each hospital, and a third-party statistics agent rechecked all entries. In case of extreme or missing values, the data were rechecked by the project coordinator of each hospital.

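### Do the chi-square and log-rank tests need a hospital term because allocation was not stratified by hospital?

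*Protocol*

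**What the plan says.** Protocol section 2.4 describes one computer-generated sequence for all 330 patients. It says that "the envelopes were sorted by random sequence and evenly distributed among the six selected hospitals", which is 330/6 = 55 per hospital, and that "Three different study groups with equal numbers of participants (n=110) were established using this non-stratified random allocations". No stratification factor of any kind is named.

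Much of the conduct is local. Under section 2.5.2, "each hospital assigned two senior IV nurses for MC puncture". Under section 2.7, "bedside nurses evaluated and recorded catheter functioning and complications daily". Section 2.8 limits differences between sites through one catheter brand and batch, "a unified catheter placement and maintenance process", common criteria for appointing the specialist nurses, and central rechecking of entries.

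The SAP is a single paragraph. For the main outcome (patients with at least one complication, section 2.6.1) it says: "Counting data were compared using the Chi-square test, exact probability method, and Kruskal-Wallis H test". For the cumulative event curves it says that "differences in these rates were assessed using log-rank tests". Neither test has a hospital stratum or covariate, and no table by hospital is listed.

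**The concern.** The arm split inside each hospital is left to chance, and complication rates may well differ between hospitals, because each has its own inserters, ward nurses and recorders. If one arm happened to draw more patients from a high-rate hospital, part of the observed difference would reflect hospital rather than tip position. A test that ignores hospital would not show this. At stake would be a spurious or masked difference between arms, or some loss of power. In many multicentre trials site is a routine stratification factor, so its absence from both the allocation and the analysis draws attention.

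**Working it through.** **Inputs.** 330 patients, three arms of 110, six hospitals of 55 (section 2.4). Complication rates 32.5% and 12.5% (section 2.3), mean 22.5%. Overall alpha 0.05 two-sided, pairwise 0.017, log-rank threshold P<0.0001 (SAP). The documents give no between-hospital variation, so its standard deviation σ (log-odds scale, or log-hazard scale for log-rank) is assumed over a range.

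**The plan's own figure.** Section 2.3 gives 65 per group. With pooled variance and one-sided 0.05, n = (1.645 + 0.842)² × 2 × 0.225 × 0.775 / 0.20² = 53.9, and 53.9 × 1.2 = 64.7, so 65. (Two-sided 0.05 gives 68.4 × 1.2 = 82.1.) The 110 per arm enrolled exceeds both, and the checks below use 110.

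**Step 1: how uneven can the arms be?** The count of one arm in a hospital has mean 55/3 = 18.3 and variance 55 × (1/3) × (2/3) × (275/329) = 10.2, so SD 3.2, with a 95% range of 12 to 25. Chance imbalance is real.

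**Step 2: what does it do to the difference between two arms?** For hospital rates p_h, the shift from hospital mix has SD of about σ × 0.225 × 0.775 × √(2/110) × √(275/329) = 2.15σ percentage points. That is 0.9, 1.3 and 2.1 points for σ = 0.43, 0.6 and 1.0. Simulation gives 0.9, 1.2 and 1.8 (the linear formula runs high at large σ), with 95th percentiles of absolute size of 1.7, 2.4 and 3.8. At σ = 1.0, the 10th to 90th percentile of hospital rates is already 6% to 45%.

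**Step 3: is this shift extra to the test's error?** No. The chi-square test uses the variance p(1 − p) at the pooled rate p, and

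p(1 − p) = mean of p_h(1 − p_h) + mean of (p_h − p)².

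The second term is the hospital variation, so it is already counted. The SD of a difference under no effect is √(2 × 0.225 × 0.775/110) = 5.6 points. The mix components of 0.9, 1.2 and 1.8 are about 3%, 5% and 10% of that variance, inside it and not on top of it. Under a single random list, the chance distribution of the arm difference depends on the total number of events, not on which hospital they came from.

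**Step 4: type I error by simulation.** For σ = 0, 0.4, 0.8 and 1.2, the three-group chi-square test at 0.05 rejects in 4.9%, 5.1%, 5.4% and 5.3% of null trials. The hospital-stratified Cochran-Mantel-Haenszel (CMH) test rejects in 4.9%, 4.8%, 5.1% and 5.0%. Log-rank at 0.05 rejects in 4.8%, 5.1%, 4.9% and 5.8%, and stratified log-rank in 4.9%, 5.1%, 4.8% and 6.0%.

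**Step 5: power.** Pairwise, 32.5% against 12.5%, 110 per arm, alpha 0.0167:

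| σ | Chi-square | CMH by hospital | Change |
|---|---|---|---|
| 0 | 89.6% | 88.2% | -1.4 |
| 0.43 | 89.2% | 88.8% | -0.4 |
| 0.6 | 89.1% | 89.7% | +0.6 |
| 1.0 | 88.6% | 91.0% | +2.4 |

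Stratifying removes the hospital term of Step 3 but pays for uneven arms within hospitals, so the sign changes between σ of about 0.4 and 0.6. With 88 per arm (110 less the 20% loss allowance) and σ = 0, power is 80.4% against 78.5%, a loss of 1.9 points.

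For the three-group test with an assumed third-arm rate of 32.5%, the change is from -0.2 points (96.6% to 96.4%, σ = 0) to +1.9 points (95.5% to 97.4%, σ = 1.2).

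**Step 6: log-rank at the SAP's own threshold.** With exponential times, 14-day risks of 12.5/32.5/32.5% and censoring uniform on days 5 to 21 (all assumed), power at P<0.0001, plain against stratified, is 29.9% and 28.4% at σ = 0, 29.0% and 29.6% at 0.4, 19.2% and 25.2% at 0.8, and 10.1% and 20.6% at 1.2.

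**The case for a change.** The best case for a hospital stratum is that hospitals may differ a great deal, and then it helps. With smaller assumed effects (15/28/28%), three-group power rises from 67.0% to 70.4% at σ = 0.8 and from 67.4% to 74.3% at σ = 1.2. The log-rank gain at σ = 1.2 is larger still. That is correct as arithmetic. But σ = 1.2 on the log-hazard scale puts the 90th-percentile hospital at exp(2 × 1.28 × 1.2), about 22 times the hazard of the 10th. Nothing in the documents points there, and the standardisation in section 2.8 points the other way. The low log-rank power in Step 6 comes mainly from the 0.0001 threshold, which is a separate matter.

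A second argument is transparency: a reader of a six-hospital trial may want arm counts and events by hospital. Such a table costs no power, and the data are evidently held by site, since "One researcher was assigned to check the data entries from each hospital". This stands as a reporting preference. The SAP lists no table layouts at all, so the absence of this one says little.

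Timing also limits the benefit. Section 2.1 places the study between September 2020 and January 2021, and the SAP is dated April 30, 2021. A stratified test added after that would most likely be a sensitivity analysis that leaves the primary result as it is.

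**Conclusion.** The concern does not hold. Omitting hospital creates no bias and leaves type I error close to nominal. The effect on pairwise power runs from a loss of about 1.4 points to a gain of about 2.4 points for σ from 0 to 1.0, and the direction turns on a between-hospital variation the documents do not report. Competent statisticians could choose either analysis.

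This rests on the list behaving as one random split of 110/110/110 over 6 × 55 and on the assumed values of σ. It covers only the omission of hospital. It does not endorse the P<0.0001 log-rank threshold, the withdrawals after randomisation in section 2.2, the per-protocol style of analysis in the SAP, or outcome recording by staff who are not blinded. A hospital stratum would cure none of these.
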